## 17.4 Time Points to Submit CRFs

After completion of subject observation or assessment in each assessment period, the investigator (or subinvestigator) will promptly complete an entry in the eCRF within 5 days in principle.

## 18. Direct Access to the Source Data

The investigator and the head of the study site will allow direct access to all study-related data by the sponsor for monitoring and auditing, or by the IRB or regulatory authorities for inspections.

## 19. Quality Control and Quality Assurance of the Study

The sponsor shall conduct the “quality control and quality assurance of the study” to maintain the quality and reliability of the study, according to the GCP standard operating procedure of Mitsubishi Tanabe Pharma Corporation. The study site and the investigator shall cooperate with the sponsor for the quality control and quality assurance of the study.

For the quality control of the study, the monitor shall confirm that the study is being performed in compliance with the study-related procedures of the study site, latest protocol, and GCP through appropriate direct access to the source data. The monitor will also review that the CRFs provided by the investigator (or subinvestigator) are accurate and complete, and confirm that they are verifiable with study-related records such as the source data.

In order to assure implementation of the study in compliance with the protocol and GCP, the auditor shall conduct audits in accordance with the GCP standard operating procedure, in order to confirm that quality control is properly performed.

Confidential

## 20. ETHICS

### 20.1 Ethical Conduct of the Study

This study shall be conducted in accordance with ethical principles that have their origin in the Declaration of Helsinki, the Law on Securing Quality, Efficacy and Safety of Products Including Pharmaceuticals and Medical Devices, GCP, and the protocol.

### 20.2 Institutional Review Board

The IRB shall review the study from ethical, scientific, medical, and pharmaceutical perspectives to determine the implementation and continuation of the study based on the investigator's brochure, protocol, informed consent form, and written information.

### 20.3 Protection of Subject Confidentiality

When enrolling subjects and filling in the CRFs, the investigator will specify each subject using a subject ID code. In addition, subject confidentiality shall be protected at the time of direct access to the source data, publication to medical journals, and data submission to the regulatory authorities.

## 21. Retention of Records

### (1) Records to be retained at the study site

The record storage manager assigned by the head of the study site will store records related to the study at the study site until date 1) or 2) below, whichever comes later. However, when the sponsor deems it necessary to retain these records for a longer period, the storage period and method of storage shall be decided upon discussion with the sponsor.

If the sponsor decides not to attach the clinical study results collected from the study to the application for marketing approval, the sponsor will report this decision and the reason to the head of the study site in writing.

In addition, when the marketing approval of the investigational product is obtained, or when the marketing approval is not obtained and development is terminated, the sponsor will report these matters to the head of the study site in writing.

- 1) The date of marketing approval of the investigational product (date of approval for partial changes for approval for additional indications) (When development is terminated, or when a notification has been received indicating that the study results will not be attached to the application, this will be 25 years from the date of receiving the notification.)
- 2) Twenty-five years from the date of study termination or completion

### (2) Records to be retained by the sponsor

- 1) The sponsor will store records relating to the study at the sponsor until date 1) or 2) below, whichever comes later. Twenty-five years from the date of marketing approval of the investigational product (date of approval for partial changes for approval for additional

Confidential

indications) or date of completion of reexamination (When development is terminated, this will be 25 years from the date of the decision for development termination.)

- 2) Twenty-five years from the date of study termination or completion

## 22. Payment to the Subjects

Payment to the subjects and the study site will be made according to the contract or agreement between the study site and the sponsor.

## 23. Compensation for Health Hazards and Insurance

### 23.1 Compensation for Health Hazards

If any health hazards to the subjects are caused by this study, the sponsor assures appropriate compensation for such health hazards, according to the standards specified by the sponsor, except in cases where it is determined that the health hazard is not related to the study. (This compensation includes medical expenses, medical expenses <copayments>, medical allowances, and compensation money.) In such cases, the sponsor will not impose a burden on the subjects regarding proof of the relationship to the study treatment.

### 23.2 Insurance

The sponsor shall take the necessary steps, such as purchasing insurance to prepare for any possible compensation for study-related health hazards to the subjects, to exercise its compensation and restitution responsibilities.

## 24. Agreement on Publication

This protocol contains information that is confidential and proprietary to the sponsor. While this protocol is provided to persons involved in this study, such as the investigator (subinvestigator) and the IRB, no information concerning this study may be disclosed to any third party without the prior written approval of the sponsor.

When the results of this study are to be published externally, such as when the investigator (subinvestigator) or other staff of the study site present at a medical society meeting or elsewhere, prior approval should be obtained from the sponsor.

The sponsor can freely use the results of this study for the purposes of reporting to the regulatory authorities, proper use of pharmaceutical products, and marketing.

Confidential

8.2. Efficacy Assessments	16
8.3. Safety Assessments.....	16
8.3.1. Adverse Events.....	16
8.3.2. Laboratory Tests	16
8.3.3. Vital Signs.....	17
8.3.4. 12-Lead ECGs	17
8.3.5. Physical Examinations.....	18
8.4. Pharmacokinetics Evaluation.....	18
8.4.1. Concentrations for unchanged edaravone, sulfate conjugate, and glucuronide conjugate	18
8.4.2. Pharmacokinetic Parameters for unchanged edaravone, sulfate conjugate, and glucuronide conjugate	18
9. DATA PRESENTATION CONVENTIONS	19
9.1. Number of Digits to Report	19
9.2. Treatments to Report	19
9.3. Analysis Visits to Report	20
10. CHANGE FROM THE PROTOCOL.....	20
11. SOFTWARE.....	20
12. REFERENCES	20

ABBREVIATIONS

Abbreviations	Definitions
AE	adverse event
ALS	amyotrophic lateral sclerosis
ALT	alanine transaminase
ALP	alkaline phosphatase
AST	aspartate transaminase
BLQ	below limit of quantification
BMI	body mass index
CI	confidence interval
CV	coefficient of variation
DP	decimal places
DRM	data review meeting
ECG	electrocardiogram
MedDRA	medical dictionary for regulatory activities
MTPC	Mitsubishi Tanabe Pharma Corporation
PEG	percutaneous endoscopic gastrostomy
PK	pharmacokinetics
PKPOP	pharmacokinetics analysis set
PT	preferred term
SAP	statistical analysis plan
SAE	serious adverse event
SAF	safety population
SD	standard deviation
SOC	system organ class
TEAE	treatment emergent adverse event
TESAE	treatment emergent serious adverse events
WHO	World Health Organization

LIST OF PK PARAMETERS

Parameters	Definitions
AUC _{0-X}	Area under the plasma concentration-time curve from zero up to X hour
AUC _{0-t}	Area under the plasma concentration-time curve from zero up to the last quantifiable concentration time point
AUC _{0-∞}	Area under the plasma concentration-time curve from zero up to infinity with extrapolation of the terminal phase
AUC% _{ex}	Area under the (plasma) concentration-time curve extrapolated from the last quantifiable concentration time point to infinity in % of the total AUC _{0-∞}
Ae _{0-X}	Cumulative urinary excretion amount of drug from zero to X hour
C _{max}	Maximum plasma concentration after administration
C _{last}	Last quantifiable concentration
CL/F	Apparent total clearance
CL _R	Renal clearance
k _{el}	Elimination rate constant from the central compartment
LLOQ	Lower limit of quantification
LOQ	Limit of quantification
MRT	Mean residence time
NC	Not calculated
t _{1/2}	Terminal elimination half-life in plasma concentration-time course
V _{ss/F}	Apparent volume of distribution at steady state
V _{z/F}	Apparent volume of distribution during terminal phase
Ae%	Urinary excretion ratio of drug

1. INTRODUCTION

This statistical analysis plan (SAP) is based on the final protocol (v1.0) dated 1-Nov-2019. The plan covers statistical analysis, tabulations and listings of the study data to investigate the pharmacokinetics (PK) and safety. The study is evaluable in 6 subjects and may be completed before a sample size of 9 subjects is reached.

The SAP is prepared by Mitsubishi Tanabe Pharma Corporation (MTPC). The statistical analysis and production of the outputs described in the SAP and QC will be conducted by [REDACTED]. The final analysis and outputs will be checked and approved by MTPC Data Science Department.

Any statistical analysis details described in this document supersede any description of statistical analysis in the protocol.

2. STUDY OBJECTIVE AND ENDPOINTS

2.1. Study Objective(s)

To evaluate the PK of single doses of edaravone oral suspension in amyotrophic lateral sclerosis (ALS) patients with percutaneous endoscopic gastrostomy (PEG).

2.2. Safety Assessments

- (1) Adverse events and adverse drug reactions
- (2) 12-lead ECG
- (3) Laboratory tests
- (4) Vital signs

2.3. Pharmacokinetic Assessments

- (1) Drug concentration (in plasma and urine)

Unchanged edaravone, sulfate conjugate, and glucuronide conjugate

- (2) Pharmacokinetic parameters

Unchanged edaravone: AUC_{0-t}, AUC₀₋₂₄, AUC_{0-∞}, C_{max}, t_{max}, t_{1/2}, k_{el} MRT, CL/F, V_z/F, V_{ss}/F, Ae, Ae%, CL_R

Sulfate conjugate and glucuronide conjugate: AUC_{0-t}, AUC₀₋₂₄, AUC_{0-∞}, C_{max}, t_{max}, t_{1/2}, k_{el}, Ae, Ae%

Sum of unchanged edaravone and metabolites: Ae%

(t: Final concentration measurable time point)

Other PK parameters (for all PK profiles for which the k_{el} has been calculated): AUC%_{ex}, Adjusted R², Number of k_{el} points, Lower limited of k_{el}, Upper limiter of k_{el}

3. STUDY DESIGN

3.1. Phase and Type of the Study

Phase of the study: Phase I

Type of the study: Clinical pharmacology study

3.2. Study Design

3.2.1. Type and Details of Cohorts

Single-dose, open-label

3.2.2. Study Period and Evaluation Period

Study period: The study period is defined as the period from the time of obtaining the informed consent to the time of completion of the end-of-study assessment or discontinuation assessment (for subjects who have entered into the follow-up period, to the time of completion or termination of the follow-up). A required hospitalization period is from Day -1 to Day 2.

Evaluation period: The evaluation period is defined as the period from provision of informed consent to completion of the end-of-study assessment or discontinuation assessment.

Screening: Subjects providing informed consent will be screened for eligibility to select subjects meeting all of the inclusion criteria and none of the exclusion criteria.

End-of-study assessment: The prespecified observations and tests will be performed as the end-of-study assessment, 7 days (allowance \pm 2 days) after the dose of the investigational product.

3.3. Schedule of Study Procedures

Day	Informed consent	Screening Day -30 to -2	Day -1	Day 1								Day 2	End-of-study ^{b)} Assessment Day 8 (±2)
Time after dosing				Pre-dose	0	15 m	30 m	1 h	2 h	4 h	8 h	24 h	
Time (For administration at 9:00 a.m.)					9:00	9:15	9:30	10:00	11:00	13:00	17:00	9:00	
Hospitalization				←								→	
Written informed consent	X												
Subject characteristics	X												
Eligibility assessment	X	X	X										
Dosing of edaravone ^{c)}					X								
Height, body weight, BMI ^{d)}	X ^{a)}	X ^{a)}										X	X
Physical examination	X	X	X									X	X
Vital signs	X	X	X									X	X
12-lead ECG	X ^{a)}	X ^{a)}	X									X	X
Laboratory tests	X ^{a)}	X ^{a)}										X	X
Serological tests	X												
Pregnancy test (only female)	X	X											X
Adverse events	←											→	
Concomitant medications	←											→	
Blood sampling for PK				X	X	X	X	X	X	X	X	X	
Urine sampling for PK ^{e)}	←											→	

- a) Subjects who are hospitalized throughout the study do not need to undergo testing on Day -1 if they undergo a preliminary test between Day -2 and Day -3.
- b) At the time of withdrawal, the same tests will be performed as those of the end-of-study assessment.
- c) After fasting for at least 10 hours, patients will receive the edaravone oral suspension via a gastric tube. Ingestion of water other than the water provided at the time of administration is prohibited from 1 hour before to 1 hour after administration of the investigational product. They will fast until the completion of blood sampling for PK performed 4 hours after the administration.
- d) Height: Screening
Body weight, BMI: Screening and Day -1
- e) Urine volume will be measured for each void. A portion of the urine will be collected, dispensed into a tube containing stabilizer, and stored frozen. Urinate will be forced to void at pre-dose and 8 hours after administration. Urine will not be collected from subjects if collection is difficult.

3.4. Sample Size and Power Considerations

9 subjects

[Rationales for setting]

The target number of subjects was set at 9 on the assumption that 6 subjects would allow obtaining results that will meet the study objectives and some subjects would drop out, although it is not based on statistical calculations.

4. PLANNED ANALYSIS

4.1. Final Analysis

This SAP will be finalized before database lock. Final data analysis will be conducted after database lock.

5. ANALYSIS POPULATIONS

PK analysis will be performed on the PK analysis set (PKPOP). Safety analysis will be performed on the safety analysis set (SAF). The definitions of the analysis sets are provided below. The detailed handling of subjects will be determined by the sponsor, by the time of the data lock.

(1) PKPOP

The PK analysis set will consist of all subjects who received at least 1 dose of the investigational product and had evaluable PK data.

(2) SAF

The SAF will consist of all subjects who received at least 1 dose of the investigational product.

6. STATISTICAL CONSIDERATIONS

6.1. Descriptive Statistics

(1) Non-PK related

Continuous data will be summarized descriptively using the number in the analysis set (N), the number of observations (n), mean, standard deviation (SD), median, minimum and maximum. Categorical data will be summarized using frequency counts and percentages. The denominator for the percentages will be the total number of subjects and analysis population being presented, unless otherwise specified.

(2) PK related

(a) Plasma concentrations

Plasma concentrations will be summarized descriptively using N, n, mean, SD, CV%, median, minimum and maximum.

(b) Pharmacokinetic parameters

The plasma and urine PK parameters will be summarized descriptively using N, n, arithmetic mean, SD, median, CV%, range (minimum, maximum), geometric mean and geometric CV%. For Ae, Ae% and CLr, geometric mean and geometric CV% will be calculated only when all the individual Ae, Ae% and CLr is greater than 0 in each sampling time point.

CV% and Geometric CV% will be calculated as follows:

$$CV\% = \frac{\text{standard deviation}}{\text{arithmetic mean}} \times 100$$

$$\text{Geometric CV\%} = \sqrt{[\exp(\sigma^2) - 1]} \times 100$$

where σ represents the standard deviation computed on the natural logarithmic transformed concentrations.

6.2. Data Review Meeting

Prior to database lock, a data review meeting (DRM) was conducted at August 31 2020. Protocol deviation and handing of subjects and records, for analysis sets and evaluations, was confirmed during DRM.

Although some protocol deviations were observed during the study, as a results of DRM, all subjects were included in SAF and PKPOP.

The PK data handling was assessed during DRM. All PK data were considered valid and included in the calculation of PK parameters and in the summary tables and figures.

7. DATA CONVENTIONS

7.1. Analysis Variable Definitions

7.1.1. Study Subjects

7.1.1.1. Demographic and Other Baseline Characteristics

(1) BMI

BMI will be recalculated using the formula below and reported to 1DP. The BMI on Day -1 will be calculated based on the height at screening and body weight on Day -1.

$$\text{BMI (kg/m}^2\text{)} = \text{weight (kg)} / \{\text{height (m)}\}^2$$

(2) Age at informed consent

Age (year) = year of informed consent – year of birth

Subtract 1 from the age (years) calculated above, if [Month of informed consent < Month of birth] or [Month of informed consent = Month of birth AND Day of informed consent < Day of birth].

7.1.1.2. Medical History

Medical history will be coded according to the MedDRA version 22.1.

7.1.1.3. Prior or Concomitant Medication/ Therapy

Medications will be coded according to the WHO Drug Dictionary (WHO-DD) Global B3 Format September 1, 2019.

(1) Prior Medication/ Therapy

Prior medication/ therapy is any medication/ therapy that was stopped prior to the investigational product administration.

(2) Concomitant Medication/ Therapy

Concomitant medication/ therapy is any medication (including commercially available drugs) / therapy other than the investigational product, between the start of investigational product administration and completion of the end-of-study assessment.

7.1.2. Safety Assessments

7.1.2.1. Adverse Events

Adverse events will be coded according to the MedDRA version 22.1.

(1) Treatment Emergent Adverse Events/ Treatment Emergent Serious Adverse Events (TEAEs/TESAEs)

An AE/SAE is classified as treatment emergent if it newly occurred after the first dose of investigational product or if a pre-dose event increases in severity following the first dose of investigational product.

(2) Adverse Drug Reaction

A TEAE is considered “adverse drug reaction” if it has been assessed as having a “reasonable possibility” in relationship to the investigational product.

(3) Time to Adverse Events

Time to Adverse Events occurrence (days) = AE start date – date of first administration + 1

(4) Duration of Adverse Events

Duration of Adverse Events (days) = AE stop date – AE start date + 1

7.1.2.2. Laboratory Tests

Values for out of pre-defined clinically relevant will have clinically relevant values flagged set (L=Lower than normal range, H=Higher than normal range or A=Abnormal).

7.1.2.3. 12-Lead ECG

(1) Criteria for pre-defined limit

12-lead ECG:

- QTcF > 500msec
- 500 >= QTcF > 480msec
- 480 >= QTcF > 450msec
- QTcF <= 450 msec
- Change from baseline in QTcF > 30 msec
- Change from baseline in QTcF > 60 msec

7.1.3. Pharmacokinetics Evaluation

7.1.3.1. Plasma Concentration

For the calculation of the summary statistics, concentration values reported as below the limit of quantification (BLQ) will be set to 0.

7.1.3.2. Pharmacokinetic Parameters

For the calculation of PK parameters, actual sampling time (in hours rounded to 2 DPs) relative to dosing should be used. If sampling time is before the time of dose, time after dose will be set

to 0. When k_{el} is missing (or cannot be determined), $t_{1/2}$, $AUC_{0-\infty}$, $AUC\%_{ex}$, CL/F , MRT , V_z/F and V_{ss}/F will not be calculated. Pharmacokinetic parameter of V_{ss}/F will be calculated as follows:

$$V_{ss}/F = MRT \times CL/F$$

(1) Below the limit of quantification

Concentration below the limit of quantification (BLQ) will be imputed with a value of 0. For calculation of AUCs, missing data will be treated as if the respective sample had never been scheduled for the calculation by the linear-linear trapezoidal rule. For the calculation of Ae in each sampling intervals, BLQ concentration in urine will be set to 0.

(2) Urinary parameters

Urinary parameters will be calculated as follows:

$$Ae = Concentration \times Volume \text{ of urine}$$

$$Ae\%_{0-x} = Ae_{0-x} / Dose$$

$$CL_R = Ae_{0-x} / AUC_{0-x}$$

For metabolites, Ae converted to the amount equivalent to unchanged edaravone will be used in the calculation of $Ae\%$. $Ae\%$ of sum of unchanged edaravone and its metabolites will be calculated as the sum of $Ae\%$ of each analyte.

7.2. Analysis Visit Definitions

(1) Non-PK related

The date of the first dose of investigational product is defined as Day 1.

Unless otherwise specified, baseline will be the last observed value of the parameter of interest prior to the first intake of investigational product (this includes unscheduled visits).

Tests	Analysis visit	Nominal day/Time point	Window
Vital signs 12-lead ECG	Screening	Day -30 to Day -2	-
	Day -1	Day -1	-
	Day 1	Before initiation of study treatment on Day 1	-
	Day 2	24 hours after initiation of study treatment	Nominal time point \pm 3 hours
Laboratory tests	Screening	Day -30 to Day -2	-
	Day -1	Day -1	Day -2 to Day -3 when subjects who are hospitalized throughout the study undergo a preliminary test between Day -2 and Day

Tests	Analysis visit	Nominal day/Time point	Window
			-3. Day -1 if otherwise.
	Day 2	Day2	-

(2) PK related

The allowable time window will be the following.

Plasma PK sampling

Nominal Time Point	Window
Predose	Within 60 min before dosing
0.25, 0.5, 1, 2, 4, 8 h after dosing	Nominal time point \pm 5 min
24 h after dosing	Nominal time point \pm 15 min

Urine PK sampling

Nominal Time Point	Window
Predose	Within 60 min before dosing
Voluntary Urine	—
Forced micturition at 8 h after dosing	Nominal time point \pm 30 min

7.3. Data Handling Convention for Missing Data

(1) Non-PK related

Adverse events:

If severity or relationship is found to be missing the most severe occurrence will be imputed for the summary of interest.

For AE start missing or partial dates, the AE will be treated as TEAE if it cannot be determined to be a non-TEAE.

Other safety:

For safety summaries, only observed data will be used. Unless otherwise specified, missing safety data will not be imputed.

(2) PK related

For PK summaries, only observed data will be used. Missing PK data will not be imputed.

When summing total Ae and Ae%, missing Ae and Ae% in each interval will be imputed to 0.

If Ae and Ae% in all intervals of a subject are missing then total Ae and Ae% of the subject will be NC.

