### 9.2.4 Pharmacokinetic assessments

Blood sampling will be performed for measurement of plasma concentrations of unchanged edaravone, sulfate conjugate, and glucuronide conjugate, and urine sampling will be performed for measurement of urine concentrations of them. The investigator (or subinvestigator) or study collaborator will record the dates and times of the blood and urine sampling and the sampled urine volume in the CRF. The measurement will be conducted in the drug concentration measurement site. The acceptable time range for the time of each blood or urine sampling (forced void) will be specified in a separate document.

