###### (c) Volume of blood sampling: 5.5 mL, Total: 44 mL (per subject)

#### 9.2.4.2 Measurement of urine concentrations of unchanged edaravone, sulfate conjugate, and glucuronide conjugate

From pre-dose to 8 hours after investigational product administration, urine volume will be measured at voiding and the urine specimen will be processed (see Section 9.2.4.3). Urinate will be forced to void at pre-dose and 8 hours after administration. Urine will not be collected from subjects if collection is difficult.

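### SAP 7.3(2) totals a missing urine interval as 0 without separating no urine passed from urine passed but not measured, so a partial sum could be reported as full 0–8 h Ae and Ae%

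*SAP*

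**What the plan says.** Protocol section 9.2.4.2 sets the collection period: "From pre-dose to 8 hours after investigational product administration, urine volume will be measured at voiding and the urine specimen will be processed". Forced voids are planned at pre-dose and at 8 h. The same section adds: "Urine will not be collected from subjects if collection is difficult". Under section 9.2.4, site staff "record the dates and times of the blood and urine sampling and the sampled urine volume in the CRF".

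The SAP's list of PK parameters defines Ae0-X as: "Cumulative urinary excretion amount of drug from zero to X hour". Section 7.1.3.2(2) obtains Ae% by dividing Ae by dose, summed Ae% by adding the three analytes' Ae%, and CL_R by dividing Ae0-x by AUC0-x.

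Section 7.3(2) first says that missing PK data are not imputed. It then makes an exception for urine totals: "When summing total Ae and Ae%, missing Ae and Ae% in each interval will be imputed to 0". One limit follows: "If Ae and Ae% in all intervals of a subject are missing then total Ae and Ae% of the subject will be NC".

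**The concern.** A missing interval value can mean two things. If no urine was passed, the amount for that interval is truly 0, and drug still in the bladder appears in the next void. If urine was passed but its volume or concentration is missing, the amount is unknown and probably above 0. The rule gives both cases 0.

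In the second case the total covers only part of the period, yet it is presented as the cumulative 0–8 h amount. The error can only be downward. The SAP has no completeness criterion, flag or exclusion for such a total.

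The stake is limited to Ae, Ae%, summed Ae% and CL_R. Plasma parameters are untouched, and no test or comparison uses the urinary values.

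**Working it through.** The plan gives no figure to reproduce, so the check is whether another rule covers the case, followed by an illustration of size.

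**1. Does another rule cover it?**
- Below-quantification urine has its own rule in SAP 7.1.3.2(1): "For the calculation of Ae in each sampling intervals, BLQ concentration in urine will be set to 0". The 7.3(2) sentence therefore concerns values that are truly missing.
- The NC limit needs every interval to be missing. It covers a subject with no urine collected, not one with a partly lost collection.
- Protocol section 13.3 lets a meeting decide on problem data, but its itemised PK list covers blood and plasma only. SAP section 1 also says that SAP analysis details take precedence over the protocol.

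**2. The rule applied, in arbitrary units, pre-dose interval first**
- Complete: 0 + 40 + 25 + 20 = 85.
- The 40-unit void passed but not measured: 0 + 0 + 25 + 20 = 45. The reported total is (85 − 45)/85 = 47% too low.
- All intervals missing: NC.
- Pre-dose observed as 0 and every post-dose interval missing: read literally, the total is 0 rather than NC, because the SAP does not say whether pre-dose counts among all intervals. Section 6.1 gives geometric statistics for urinary parameters only when all individual values exceed 0, so one such false zero would remove them for the group.

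**3. Effect on group means**

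Assumptions: one affected subject, equal true values, lost share L of 25%, 33% or 50%. None of these comes from the documents. The values n = 6 and n = 9 are the sufficient and target numbers in SAP 3.4.

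Arithmetic mean change = −L/n. Geometric mean change = (1 − L)^(1/n) − 1. For example, with L = 0.50 and n = 6: −0.50/6 = −8.3%, and 0.50^(1/6) − 1 = −10.9%.

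| L | n = 6 arithmetic | n = 6 geometric | n = 9 arithmetic | n = 9 geometric |
|---|---|---|---|---|
| 25% | −4.2% | −4.7% | −2.8% | −3.1% |
| 33% | −5.5% | −6.5% | −3.7% | −4.4% |
| 50% | −8.3% | −10.9% | −5.6% | −7.4% |

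The affected subject's own Ae and Ae% fall by the full L.

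**4. Is that range of L plausible?**

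Assume mono-exponential excretion and voids at 2, 4 and 8 h. Take metabolite half-lives of 2.8 to 7.9 h from the Study MT-1186-J01 results in protocol section 1. With k = ln 2 / half-life, the share of the 0–8 h amount in a void covering a to b hours is (e^(−ka) − e^(−kb)) / (1 − e^(−8k)). The first void holds about 32% to 45%, the second 27% to 28%, and the last 27% to 41%. These shares lie within the assumed 25% to 50%.

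**5. Derived quantities**

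A missing volume affects all three analytes; a missing concentration affects only its own analyte. Summed Ae% is understated by the lost part of its total. CL_R of unchanged edaravone falls by the same share as its Ae if the AUC stays at 0–8 h. The SAP does not state x.

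**The case against.** The strongest defence is that the rule has a correct everyday use. Voluntary voids have no scheduled time or window in SAP 7.2, so empty intervals are expected and 0 is then the true amount. The rule is explicit and comes with an NC limit. This stands: the fault is a missing distinction, not the use of zero as such.

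Second, no effect is documented. SAP 6.2 reports that the data review meeting of 31 August 2020 accepted all PK data as valid and included them. A reader might infer from the rule that the reported urinary results are too low. The documents do not support that, because nothing shows that any void was lost. The opposite inference, that collections were complete, is not supported either: accepting the data obtained does not say that every void was captured.

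Third, the protocol's allowance for difficult collection might be read as planning for partly lost collections. It speaks of not collecting from a subject, which the NC limit handles.

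Fourth, the SAP does not say whether each voluntary void is its own interval or several are pooled. Treating an interval as one void is an assumption. If voids are pooled, a lost one may leave the interval value non-missing and the shortfall would not come from the zero rule. The repair must therefore refer to voids as well as intervals.

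Finally, urinary parameters are to be listed (SAP 8.4.2), so a gap might be noticed. Nothing requires the total to be marked incomplete.

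**Conclusion.** The point holds as a conditional and minor one. When a post-dose void is passed but its volume or concentration is missing, the rule as written turns an unknown amount into 0 and reports a partial sum as the 0–8 h total. This rests on at least one other interval being observed and, for the zero rule itself to act, on the lost void making its interval value missing.

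The affected subject loses the full share. The group means in the table fall by 2.8% to 10.9%, depending on the assumed share, the number of subjects and the type of mean. These are illustrations and do not estimate an error in this study; if no void was lost, the effect is 0.

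A reader might extend the concern to the study's main PK results. The documents do not support that, since plasma Cmax and AUC do not use urine data.

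**What to change.** Replace the zero-imputation sentence in SAP 7.3(2) with:

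> An interval in which no urine was passed contributes 0 to total Ae and Ae%. If any post-dose void, voluntary or forced, is recorded as passed but its volume or concentration is missing (including one of several voids pooled in an interval), total Ae and Ae% of each affected analyte, the summed Ae%, and CL_R of unchanged edaravone if affected, are NC for that subject; the partial amounts are listed with a flag and excluded from the summaries. All-intervals-missing refers to post-dose intervals only.

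Where source records do not show whether the 8 h forced void was empty or not done, flag the total as possibly incomplete rather than setting it to NC. An attempted but empty void is a true 0, and the protocol does not show that such attempts are recorded.

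The NC condition can use the sampling dates, times and volumes already collected in the CRF, together with the laboratory's concentration results. If the data are already locked, protocol section 13.5 requires the change and its reason in a revised SAP and the study report, with results before and after kept apart.

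There are two costs. The urinary summaries may lose subjects, which matters with 6 to 9 people, although the flagged listing keeps the partial amounts visible. Voluntary voids that were never recorded remain undetected, so the repair is not complete.
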